4.1.1.3 Primary Definition of Progression-Free Survival (PFS)

PFS will be primarily analyzed applying an intent-to-treat (ITT) definition that utilizes all of the data on each randomly assigned subject at the time of the PFS analysis. PFS will be defined as the time from randomization to the date of the first documented tumor progression or death due to any cause. Clinical deterioration will not be considered progression. A subject who neither progresses nor dies will be censored on the date of their last adequate tumor assessment. A subject who does not have any post-baseline tumor assessments and who has not died will be censored on the date of randomization.

4.1.1.4 Secondary Definition of Progression-Free Survival

PFS will also be analyzed after censoring patients who either received subsequent therapy or had two or more missing tumor assessments prior to their disease progression or death. In this secondary definition, PFS will be measured as the time in months from randomization to the date of the first documented tumor progression or death due to any cause, provided death does not occur more than 10 weeks (2 or more assessment visits) after the last tumor assessment. Clinical deterioration will not be considered progression.

The following censoring rules will be applied for this definition of PFS:

- Subjects who receive subsequent anti-myeloma therapy prior to documented progression will be censored on the date of the last adequate tumor assessment prior to the initiation of the new therapy.
- Subjects who have an event (documented progression or death) > 10 weeks (2 assessment visits) after the last prior adequate tumor assessment will be censored at the last prior assessment.
- Subjects who neither receive subsequent therapy prior to progression nor have a progression event (including death) will be censored at their last adequate tumor assessment.
- In addition, subjects who do not have any post-baseline adequate tumor assessments and who do not die within 10 weeks of randomization will be censored on the date of randomization.

In all cases, if there are no adequate assessments for censoring then the patient is censored on the randomization date.

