5.4.2 Laboratory Assessments for Myeloma

All laboratory efficacy assessments must be performed until disease progression or withdrawal of consent, even if the subject is discontinued from study therapy and has started new myeloma therapy. Confirmation of \geq PR is required on 2 consecutive assessments for Serum, Urine and sFLC.

- 1) **Serum:** SPEP for M protein quantification, total serum protein, serum immunofixation, and quantitative immunoglobulin assay.
 - a. Serum Immunofixation is required at baseline and to confirm CR regardless of whether measurable M-protein was present at baseline.
 - b. Subjects with measurable disease in SPEP will be assessed for response based on SPEP and not by the serum FLC assay.
 - c. Subjects with measurable disease in both SPEP and UPEP will be assessed for response based on these two tests and not by the serum FLC assay.
 - d. All other serum tests will be followed at each tumor assessment.
- 2) **Serum free light chain (sFLC):**
 - a. Subjects without measurable serum M-protein (ie, < 0.5 g/dL (5 g/L)) or urine M-protein (ie, < 200 mg (0.2 g) per 24 hours) and considered oligosecretory must have sFLC assessed at each cycle until until progression.
 - b. Serum must be collected at screening and time of serum and urine IFE negativity to confirm CR and be sent to the central lab for sFLC analysis. This measurement is required to assess for sCR
- 3) **Urine:** 24-hour urine collection for M protein quantification, urinary light chains, and immunofixation. 24-hour urine must be collected with each cycle for all subjects.
 - a. Urine Immunofixation is required at baseline and to confirm CR, regardless of whether measurable M-protein was present at baseline.
 - b. All other urine tests will be followed at each tumor assessment.
- 4) **Bone marrow aspiration/biopsy:**

Table 5.4.2-1: Bone Marrow Samples		
Sample	Local Laboratory	Central Laboratory

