4 ENDPOINTS

4.1 Endpoint Definitions

4.1.1 Progression-Free Survival

4.1.1.1 Definition of an Adequate Tumor Assessment

In the analysis of PFS, subjects who do not progress are censored. A non-progressing subject can be censored on the date of a tumor assessment only if there is sufficient information to rule out progression. An “adequate” tumor assessment visit for ruling out progression will require the following information:

- Serum monoclonal paraprotein results, if measurable at baseline by central lab, and
- Urine monoclonal paraprotein results, if measurable at baseline by central lab.

- Serum free light chain results, if measurable at baseline by central lab. This is only relevant for subjects who do not have measurable serum and urine monoclonal paraprotein results.

4.1.1.2 Date of Progression or Censoring When Different Components of a Per Time Point Tumor Assessment Conducted at Different Times

As different tumor measurements may be conducted on different days, for instance, the blood draw for serum M-protein may be on a different date than 24-hour urine, the investigators were instructed to report the earliest date of the measurements associated with that time point for progression. In contrast, if tumor measurements are done on different dates and the subject is being censored, instructions were to report the latest date of the measurements associated with that time point.

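### The fourth censoring rule of the secondary PFS definition (SAP 4.1.1.4) excepts early death but not documented progression, and so conflicts with the event definition in the same section

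*SAP*

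**What the plan says.** SAP 4.1.1.4 opens with the event: "PFS will be measured as the time in months from randomization to the date of the first documented tumor progression or death". The only proviso in that sentence concerns a death more than 10 weeks after the last assessment. Four censoring rules follow:

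1. Subsequent therapy before progression: censor at the last adequate assessment before that therapy.
2. A late event: "Subjects who have an event (documented progression or death) > 10 weeks (2 assessment visits) after the last prior adequate tumor assessment" are censored at the prior assessment.
3. Neither subsequent therapy nor a progression event, with death expressly included: censor at the last adequate assessment.
4. In addition, "subjects who do not have any post-baseline adequate tumor assessments and who do not die within 10 weeks of randomization will be censored" at the randomization date.

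A closing sentence supplies a default date: "In all cases, if there are no adequate assessments for censoring then the patient is censored on the randomization date".

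Adequacy is defined in SAP 4.1.1.1, where its purpose is stated: "A non-progressing subject can be censored on the date of a tumor assessment only if there is sufficient information to rule out progression". An adequate visit needs serum paraprotein if measurable at baseline, and also "Urine monoclonal paraprotein results, if measurable at baseline by central lab". Free light chains are needed only where neither paraprotein is measurable.

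Protocol 8.3.1.2 gives the same secondary definition with three censoring rules and no counterpart to the fourth. The primary definition (SAP 4.1.1.3) censors at randomization only where there is no post-baseline assessment at all and no death.

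**The concern.** Adequacy asks whether there is enough information to rule progression out. Progression can be established on less: a rise in serum M-protein alone, imaging or corrected calcium. The fourth rule nevertheless makes the existence of an adequate visit a condition for staying uncensored, and relaxes it only for death within 10 weeks. The third rule expressly leaves out subjects with a progression event; the fourth does not.

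A programmer who codes the four rules as listed will turn some documented early progressions into censorings with zero follow-up. One who codes from the opening sentence will keep them. The two event counts and Kaplan-Meier curves would differ, and the SAP does not say which is meant. The affected results are the PFS sensitivity analysis (7.5.1), the secondary-definition versions of the supportive PFS analyses (7.5.1.1), and four topline outputs (8.7): the secondary-definition analysis, its Kaplan-Meier plot, its covariate-adjusted analysis and its forest plot.

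**Working it through.** **1. The rules applied to cases.** Serum and urine M-protein are both measurable at baseline unless stated. The second rule does not name a reference when no post-baseline visit is adequate; baseline is assumed here.

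| Case | Opening sentence and second rule | Fourth rule, literally |
|---|---|---|
| A. Serum progression at week 4, confirmed at week 8, both urines missing, alive at week 10 | Event at week 4 | Censored at day 0 |
| B. As A, but serum and urine complete at one of the two visits | Event at week 4 | Does not apply; event stands |
| C. As A, but the subject dies at week 9 | Event at week 4 | Does not apply; event stands |
| D. Urine not measurable at baseline, serum complete, urine never collected | Event at week 4 | Does not apply; visits are adequate |
| E. No adequate visit, first progression at week 16 | Removed: 16 > 10 weeks | Censored at day 0 as well |

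The conflict is confined to case A and its equivalents, such as progression on imaging or calcium when every serum and urine set is incomplete. A and C together show that, read literally, whether a week-4 progression counts depends on a later death.

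**2. The plan's design figure, for scale.** Inputs from SAP 5.1: 71 events, HR 0.57, two-sided alpha 0.2, power 85%. Equal allocation is assumed, since the visible text gives no ratio.

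- Schoenfeld: 4 × (1.2816 + 1.0364)² / (ln 0.57)² gives 69 events.
- Freedman: (1.57/0.43)² × (1.2816 + 1.0364)² gives 72 events.
- Power with 71 events: Φ(√71/2 × |ln 0.57| − 1.2816) = 0.861.

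The plan's 71 events and 85% are reproduced.

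**3. How many events could be exposed.** With exponential medians of 4.0 and 6.8 months (SAP 5.1) and 70 days = 70/30.4375 = 2.30 months:

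- Pd: 1 − exp(−ln 2 × 2.30/4.0) = 32.9%, or 18.7 of 57.
- E-Pd: 1 − exp(−ln 2 × 2.30/6.8) = 20.9%, or 11.9 of 57.
- Together about 30.6 of 114. This is an upper bound on early progressions, because it includes deaths within 10 weeks, which the rule keeps.

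The share of these with no adequate post-baseline visit is not in the documents. Under assumed shares:

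| Assumed share | Events lost of 71 | Schoenfeld power on the rest |
|---|---|---|
| 2% | 0.6 | 0.859 |
| 5% | 1.5 | 0.856 |
| 10% | 3.1 | 0.850 |
| 20% | 6.1 | 0.837 |

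**4. Effect on the hazard ratio.** Simulation: 114 subjects, 13 per month, analysis at the 71st event, 4,000 runs, unstratified, HR 0.57 (so an E-Pd median of 4.0/0.57 = 7.0 months). A share of events in the first 70 days is moved to day-0 censoring.

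| Share lost, Pd / E-Pd | HR before → after | Power before → after |
|---|---|---|
| 5% / 5% | 0.57 → 0.57 | 0.86 → 0.85 |
| 20% / 20% | 0.57 → 0.57 | 0.85 → 0.83 |
| 15% / 5% | 0.57 → 0.59 | 0.85 → 0.79 |
| 5% / 15% | 0.57 → 0.55 | 0.85 → 0.88 |

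Equal proportional loss leaves the hazard ratio where it was. Unequal loss moves it in either direction.

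**The case against.** The best defence is that the fourth rule was never meant for progressors. It follows the rule for subjects without an event, it resembles the primary definition's sentence on subjects with no post-baseline assessment, and 4.1.1.1 ties adequacy to non-progressing subjects. The closing sentence says where to censor, not whom. On that reading nothing is lost. This is a plausible account of the intent, so a reader who infers that the SAP has settled on censoring documented progressors goes too far: its sentences conflict. But the fourth rule is introduced as an additional operative rule and states its exception explicitly, so context does not remove the conflict.

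The rarity argument largely stands. The protocol requires that "24-hour urine must be collected with each cycle for all subjects", urine matters only if measurable at baseline, and SAP 7.2.2 notes that progression needs confirmation, so a further visit is expected. One complete post-baseline visit takes the subject out of the rule. The inference that a single missing urine result costs a subject the event is therefore wrong.

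A reader might also infer that persistently missing urine loses an event at any time because of this rule. Later events are already removed by the second rule (case E), in line with the section's aim of censoring after two or more missed assessments. Rewording the fourth rule would not restore them.

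The absence of the rule from protocol 8.3.1.2 is weak evidence of error. The protocol does not say what happens when no adequate assessment exists, and a SAP may fill that gap.

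**Conclusion.** The point holds as a drafting conflict that gives a wrong result if the fourth rule is applied as written: progression documented within 10 weeks of randomization becomes a day-0 censoring when every post-baseline visit lacks a required serum, urine or free light chain result.

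The number affected is probably small and cannot be derived from the documents. The range of 0.6 to 6.1 of 71 events rests on assumed shares of 2% to 20%, 57 subjects per arm and the SAP's exponential medians.

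It is tempting to infer that the rule biases the comparison because more early progressors are expected on control. That is not shown: equal proportional loss left the hazard ratio at about 0.57, and nothing in the documents indicates that such missingness differs between arms.

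The primary PFS analysis is untouched, as is duration of response, which follows the primary definition (4.1.5). The supportive analyses are also run under the primary definition, with descriptive p-values. It should still be corrected before programming, because a sensitivity analysis should not depend on which of two conflicting sentences is coded.

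**What to change.** Replace the fourth rule in SAP 4.1.1.4 with wording to this effect:

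*Censor at randomization any subject who has no adequate post-baseline tumor assessment and who has neither documented progression nor death within 10 weeks of randomization.*

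Add one sentence: adequacy determines censoring dates and the reference point for the 10-week gap; it is not required of the assessment that documents progression.

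The 10-week limit treats progression as the rule already treats death and leaves later events to the second rule. The cost is two sentences of SAP text and one programming condition. No new data are needed, and the primary analysis does not change.

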4.1.2 Objective Response Rate (ORR)

The best overall response is determined as the best assessment based on all on-study efficacy data for the subject.

Objective response rate is defined as the proportion of randomized subjects who achieve a best response of stringent complete response (sCR), complete response (CR), very good partial response (VGPR) or partial response (PR) using the modified IMWG criteria as per investigator's assessment.

4.1.3 Overall Survival

Overall survival is defined as the time from randomization to the date of death from any cause. If a subject has not died, their survival time will be censored at the date of last contact ("last known alive date"). Subject will be censored on the date of randomization if they were randomized but had no follow-up.

4.1.4 Time to Tumor Response

Time to response is defined as the time, in months, from randomization to the first objective documentation of PR or better. Time to response is restricted to the randomized subjects who achieved a best response of PR or better.

4.1.5 Duration of Response

Duration of response will be restricted to the randomized subjects with objective response of PR or better. It is measured from the time, in months, that the criteria for objective response are first met until the date of a progression event (according to the primary definition of PFS). A subject with objective response who does not have a progression event will be censored at the same time they were censored under the primary definition of PFS.

4.2 Pharmacokinetic Endpoints

The serum concentrations of elotuzumab at each time point (of the sampling schedule) will be summarized. The Cmin (minimum drug concentration observed) by study day will be summarized.

4.3 Immunogenicity Endpoints

Anti-drug antibody (ADA) is an immunogenicity endpoint. ADA will be evaluated using a validated bridging ligand binding method. For subjects who are found to have anti-elotuzumab antibodies, a titer will be reported to enable a qualitative comparison between subjects and within subjects at different time points.

4.4 Safety Endpoints

The safety endpoints include serious and non-serious adverse events, laboratory evaluations, deaths, and reasons off treatment.

[REDACTED]

5.1 Progression-Free Survival

The primary objective of the study is to compare the progression-free survival between the treatment arms in all randomized subjects. The number of events and power of this study were calculated assuming an exponential distribution for PFS in each arm.

The study will require at least 71 PFS events (progressions or deaths), for a two-sided experiment-wise $\alpha = 0.2$ log-rank test, to show a statistically significant difference in PFS between the treatment arms with 85% power when the true hazard ratio of the experimental arm to the control arm is 0.57. This is equivalent to demonstrating an improvement in median PFS from 4.0 months in the Pd arm⁹ to a median PFS of 6.8 months in the E-Pd arm.¹ A total of 105 subjects are to be randomized. Assuming approximately 10% of subjects may be lost to follow-up for the primary endpoint data, an additional 9 subjects would be randomized in the study. It is estimated that it would take approximately 9 months for full accrual of 114 subjects (assuming a fixed accrual rate of 13 subjects per month) and another 6 months to obtain the required number of events.

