7.5 Efficacy

Efficacy analyses (PFS, ORR and OS) will be conducted on the population of all randomized subjects, grouped by arm assigned at randomization, unless otherwise noted.

Unless stated otherwise, whenever a stratified analysis is specified, the stratifications factors will be those used in the randomization (per IVRS), that is:

- Number of prior lines of therapy (2-3 vs. ≥ 4)
- ISS Staging at study entry (I-II vs. III)

The final analysis of PFS will occur after at least 71 progression events have been observed. This analyses will serve as the basis for the clinical study report. The final analysis of OS will be conducted after at least 78 deaths have been observed.

All p-values reported will be 2-sided. The alpha (α) level used for the two-sided CI will be same as nominal significance level for hypothesis testing ($\alpha = 0.2$). In addition two-sided 95% CI for these endpoints will also be provided. The p-values presented in the clinical study report will be rounded to the fourth decimal place. Point estimates and confidence bounds for efficacy variables will be rounded to the second decimal place.

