7.5.1 Primary Analysis of Progression-Free Survival

The primary objective of this study is to compare PFS (based on the primary definition) across the two randomized arms. A two-sided $\alpha = 0.2$ log-rank test, stratified by number of lines of prior therapy (2-3 vs. ≥ 4) and ISS Staging at study entry (I-II vs. III) will be used to compare the PFS of subjects randomized to E-Pd to that of subjects randomized to Pd.

A stratified Cox proportional hazard model for PFS with treatment arm as single covariate will be used to report the hazard ratio of E-Pd to Pd and its corresponding 80% (and 95%) CI. The stratification factors will be the same as those used in the randomization.

The PFS function for each treatment arm will be estimated using the KM product limit method and will be displayed graphically. Median PFS will be estimated via the KM curve. Two-sided 95% CI for the median PFS will be computed for each randomized arm by the Brookmeyer and Crowley method using the log-log transformation of the survivor function.

The method of Gail and Simon¹² will be used to test for a qualitative interaction between treatment and strata, number of lines of prior therapy (2-3 vs. ≥ 4) and ISS Staging at study entry (I-II vs. III). This test will be conducted at the $\alpha = 0.10$ level and using the HR as estimate for treatment effect.

The proportional hazards assumption will be assessed via the following hazard rate model, which contains a time dependent covariate:

$$\lambda(t, z) = \lambda_i(t) e^{\{(b_1 + b_2 \times [\log(t)]) \times Z\}}, \quad i = \{1 - 4\}$$

where $i = 1 - 4$ corresponds to each of the four levels the stratum can take, and Z is the treatment indicator, which is equal to 1 for the combination arm and 0 for the control arm. The transformation of time is $\log(t)$. The null hypothesis, that the proportional hazards assumption is valid, i.e., that $b_2 = 0$, will be tested against the alternative hypothesis that $b_2 \neq 0$ using a Wald statistic.

Sensitivity analyses of PFS will also be conducted based on the secondary definition of PFS. These analyses will be the same as those specified above in [Section 7.5](#), Primary Analysis of PFS.

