7.5.2 Analysis of Objective Response

The number and percentage of subjects in each category of best overall response per investigator assessment (stringent complete response [sCR], complete response [CR], very good partial response [VGPR], partial response [PR], minor response [MR], stable disease [SD], progressive disease [PD], or unable to determine [UD]) will be presented by treatment group. An estimate of the response rate and an associated exact two-sided 95% CI (Clopper and Pearson¹³) will be computed, by treatment group.

One of the secondary objectives is to compare the ORR in the two treatment groups using a two-sided $\alpha = 0.2$ level Cochran-Mantel-Haenszel (CMH) test stratified by the same factors used in the analysis of PFS. An estimate of the treatment odds ratio and corresponding two-sided 80% CI will be computed. A two-sided 95% CI will also be computed.

A 2-sided, 80% CI (along with 95% CI) for the difference of ORR between treatment arms will be computed for all randomized subjects by the method of DerSimonian and Laird¹⁴, using a fixed-effects model (setting Δ^2 equal to zero), adjusting for the stratification factors. The weighted response rate difference and 80% CI (along with 95% CI) can be determined using the following formula:

$$\hat{\theta} = \frac{\sum_{i=1}^4 \hat{\theta}_i w_i}{\sum_{i=1}^4 w_i} \sim N(\theta, 1 / \sum_{i=1}^4 w_i)$$

where $\hat{\theta}_i$ is the response rate difference of the i^{th} stratum and $w_i = 1/\text{var}(\hat{\theta}_i)$.

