7.5.3 Analysis of Overall Survival

Overall survival is another secondary objective. It will be compared between arms using a stratified log-rank test procedure with a two-sided, $\alpha = 0.2$ level. The stratification factors will be the same as those used for the analyses of PFS and tumor response. The OS function for each randomized arm will be estimated using the Kaplan-Meier product-limit method. Median and two-sided 95% confidence intervals for median OS will be computed by randomized arm.

All analyses performed for PFS (detailed in [Section 7.5.1](#)) will be repeated for OS. Supportive analyses of PFS (detailed in [Section 7.5.1.1](#)) as well as the subset analyses (detailed in [Section 7.5.1.2](#)) will also be repeated for OS.

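### SAP 5.1 labels the PFS alpha of 0.2 experiment-wise, but ORR and OS are also tested at a full two-sided 0.2 with no testing order in the visible text; read as one confirmatory family, the error is above 0.20 and up to 0.49

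*SAP*

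**What the plan says.** - **PFS, the only primary endpoint.** SAP 5.1 sizes the trial on this endpoint: "The study will require at least 71 PFS events (progressions or deaths), for a two-sided experiment-wise" alpha of 0.2, with "85% power when the true hazard ratio of the experimental arm to the control arm is 0.57". SAP 7.5.1 repeats the level: "A two-sided $\alpha = 0.2$ log-rank test, stratified by number of lines of prior therapy" and ISS stage.
- **ORR, secondary.** SAP 5.2 gives it its own power statement (at least 90% for 58% against 35%, two-sided 0.2). SAP 7.5.2 continues: "One of the secondary objectives is to compare the ORR in the two treatment groups using a two-sided" 0.2-level stratified CMH test.
- **OS, secondary.** SAP 5.3 powers it separately (75% at hazard ratio 0.64 with 78 deaths, two-sided 0.2), about 18 months after the final PFS analysis. SAP 7.5.3 says: "It will be compared between arms using a stratified log-rank test procedure with a two-sided" level of 0.2.
- **Protocol 8.4.2.2** also gives ORR and OS a two-sided 0.2 each.
- **General rule.** SAP 7.5 sets the alpha for confidence intervals to be the "same as nominal significance level for hypothesis testing", that is 0.2, and adds 95% intervals.
- **Status of p-values.** SAP 7.5.1.1 calls the p-values of the supportive PFS analyses descriptive, and SAP 7.5.2.2 gives none for time to response and duration of response. The ORR and OS comparisons carry no such label.

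None of the readable efficacy sections makes one test conditional on another or divides alpha among them.

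**The concern.** An experiment-wise level and a nominal level are different properties. The SAP uses the first term in 5.1 and the second in 7.5, both for 0.2, and the visible text does not reconcile them. ORR and OS look like inferential tests: each has a power statement and a fixed significance level, and neither is marked descriptive, although the SAP uses that label elsewhere.

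Followed as written, the visible plan lets a trial that is negative on PFS report ORR, or OS some 18 months later, as statistically significant at 0.2. A reader who had seen the label in SAP 5.1 could take that result as protected at 0.2 when it is not.

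**Working it through.** **Step 1: reproduce the plan's figure.** Inputs from SAP 5.1: two-sided alpha 0.2 (z = 1.2816), power 85% (z = 1.0364), hazard ratio 0.57. Assumption: 1:1 allocation, since the ratio is not in the visible text.

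- Schoenfeld: 4 × (1.2816 + 1.0364)² / (ln 0.57)² = 21.49 / 0.3160 = 68.0, so 69 events.
- Freedman: (1.2816 + 1.0364)² × (1.57 / 0.43)² = 5.373 × 13.33 = 71.6, so 72 events.
- At 71 events, power is 86.1% (Schoenfeld) or 84.8% (Freedman).
- A one-sided 0.2 would need only 45 to 48 events.

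The stated 71 is therefore consistent with PFS alone using the whole two-sided 0.2. Nothing is set aside for other endpoints.

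**Step 2: error over three tests when elotuzumab has no effect.** Each of PFS, ORR and OS is tested at two-sided 0.2.

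- Independent statistics: 1 − 0.8³ = 0.488. For jointly normal statistics this is the ceiling.
- False claims favouring the elotuzumab arm (E-Pd) only, 0.10 per test: 1 − 0.9³ = 0.271 if independent. This is the ceiling when correlations are not negative.
- Correlated statistics: 2 million draws of three normal statistics with a common correlation, rejecting when |z| > 1.2816. The documents give no correlation, so the first column is an assumption.

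| Assumed correlation | At least one false two-sided rejection | Excess over 0.20 | At least one false claim favouring E-Pd |
|---|---|---|---|
| 0 | 0.488 | 0.288 | 0.271 |
| 0.3 | 0.467 | 0.267 | 0.242 |
| 0.5 | 0.433 | 0.233 | 0.219 |
| 0.7 | 0.380 | 0.180 | 0.190 |
| 0.9 | 0.300 | 0.100 | 0.150 |
| 0.999 | 0.209 | 0.009 | 0.105 |

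The third column is the second minus 0.20. It is the chance that PFS is not significant while ORR or OS is. Unequal correlations give similar results: PFS–ORR 0.6, PFS–OS 0.5 and ORR–OS 0.3 give 0.434.

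Protocol 8.4.2.2 calls the OS procedure group sequential and SAP 7.5.3 does not. The calculation takes OS at 0.2 overall in either case.

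**Step 3: compare remedies.**

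- Fixed sequence starting with PFS: a later test counts only if every earlier one is significant. The family error stays at 0.20, and PFS keeps alpha 0.2 and 71 events.
- Bonferroni: 0.2 / 3 = 0.0667 per test. PFS would need 105 events for 85% power (Schoenfeld), and 71 events would give 70.3%.

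**The case against.** Four points deserve weight.

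1. **The label sits on one test.** A reader might infer that the plan promises 0.2 across PFS, ORR and OS and breaks that promise. The documents do not support this. The term appears once in the visible text, attached to the PFS log-rank test in a paragraph that sizes the trial for PFS. That test's own error is 0.20. This stands. For a single test, however, the word adds nothing, and it invites the wider reading.

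2. **Redaction.** A reader might infer that the plan has no testing order at all. Only the visible text can be judged. The synopsis statistical considerations, protocol 8.1, 8.4.2.1 and 8.5, and SAP text before 5.1 and between sections 6 and 7.2 are not readable. A fixed sequence would also show each test at a full 0.2, so the visible levels do not argue against one. This stands too. Against it, SAP 7.5, which sets the common rules for alpha and p-values, is readable, as are the ORR and OS sections, and none points to an order elsewhere.

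3. **SAP 7.5 already says nominal.** It does, but of the 0.2 level for efficacy testing in general, PFS included. It does not say that ORR and OS cannot support a claim of significance.

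4. **This is an open-label phase 2 trial with a lenient alpha and 95% intervals alongside.** Unadjusted secondary tests can be a reasonable choice in that setting. The plan should then say that this is the choice.

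**Conclusion.** The concern holds in a limited form. The visible plan tests three separately powered endpoints at a full two-sided 0.2, labels the first experiment-wise, and does not say how a significant ORR or OS is to be read when PFS fails. The PFS test itself is not inflated.

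If all three tests are read as confirmatory, the chance of at least one false two-sided rejection is above 0.20 and at most 0.49. For false claims favouring E-Pd it is at most 0.27, against 0.10 for one test. Both figures assume no treatment effect on any endpoint and jointly normal test statistics; the second also assumes correlations that are not negative.

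A reader might infer from the middle of the table that the true error is 0.38 to 0.49. That range assumes correlations between 0 and 0.7, which the documents do not give. The value 0.38 is not a floor: at 0.9 the figure is 0.30, and it approaches 0.20 as the correlation approaches 1.

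**What to change.** Unless a redacted section already does so, choose one of two changes.

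- **Fixed sequence.** Add a paragraph to SAP 7.5: PFS is tested first at two-sided 0.2, then the secondary endpoints in a stated order at the same level, each only if the one before is significant. P-values after the first non-significant test are labelled descriptive. PFS, then ORR, then OS is one example; the order of the two secondary endpoints is the sponsor's choice.
- **No hierarchy.** State that 0.2 applies to PFS only, drop *experiment-wise* from SAP 5.1, and label the ORR and OS p-values as nominal and not a basis for a claim of significance. Deleting the word alone would leave the status of ORR and OS open.

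**Cost.** Neither option needs more patients or changes the 71 events or the PFS power. Under the sequence, ORR and OS cannot be claimed formally if PFS fails, and the last endpoint cannot be claimed if the one before it fails, even when PFS succeeds. With OS last, and all three design effects true, the planned powers give a chance of a formal OS claim of 0.85 × 0.90 × 0.75 = 0.57 if the statistics are independent, and at most 0.75. With ORR last, a formal ORR claim must wait for the OS analysis. Under the second option, no formal claim on ORR or OS is available.

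### The primary PFS power statement equates HR 0.57 with medians of 4.0 and 6.8 months, but those medians give HR 0.588, for which 71 events provide about 82–83% power, not 85%

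*SAP*

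**What the plan says.** SAP Section 5.1 states the modelling basis first: "The number of events and power of this study were calculated assuming an exponential distribution for PFS in each arm". It then sets a minimum of 71 PFS events for a log-rank test at two-sided alpha 0.2, with 85% power, and translates the design hazard ratio directly into medians. The ratio of the experimental to the control arm "is 0.57. This is equivalent to demonstrating an improvement in median PFS from 4.0 months in the Pd arm", and then "to a median PFS of 6.8 months in the E-Pd arm". SAP Section 7.5 repeats 71 events as the trigger for the final PFS analysis. The protocol's sample size section is redacted, so no other visible text gives the design hazard ratio or the medians.

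**The concern.** Under an exponential model in each arm, the hazard ratio and the two medians are not separate assumptions: any two of the three fix the third. The three values in Section 5.1 do not satisfy that relation. A clinical reader will take the medians as the target effect and read the paragraph as promising 85% power for an improvement from 4.0 to 6.8 months. If the calculation was in fact done for 0.57, the promise belongs to a larger effect than the one described. The stated power and target are also what a reader will use to interpret a borderline or negative PFS result, so the two should match.

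**Working it through.** **Inputs.** All are from SAP Section 5.1 except the allocation ratio: two-sided alpha 0.2 (z = 1.2816), power 85% (z = 1.0364), 71 events, HR 0.57, medians 4.0 and 6.8 months, exponential PFS. The allocation ratio is not in the visible text; 1:1 is assumed. The SAP does not name its sample size formula, so two standard ones are used. (1.2816 + 1.0364)² = 5.373.

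**Formulas (1:1).**

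- Schoenfeld: events = 4 × 5.373 / (ln HR)²; power = Φ(|ln HR| × √events / 2 − 1.2816).
- Freedman: events = 5.373 × [(1 + HR)/(1 − HR)]²; power = Φ(√events × (1 − HR)/(1 + HR) − 1.2816).

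**Step 1: reproduce the plan at HR 0.57.** ln 0.57 = −0.5621.

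- Schoenfeld: 4 × 5.373 / 0.5621² = 68.0 events. Power with 71 events: Φ(2.368 − 1.2816) = 86.1%.
- Freedman: 5.373 × 3.651² = 71.6 events. Power with 71 events: Φ(2.308 − 1.2816) = 84.8%.

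A simulation of 20,000 trials gave 85.6% (unstratified log-rank test, exponential PFS, 114 subjects entering at 13 per month, cut at 71 events, no dropout). The plan's 71 events and 85% power are therefore correct for HR 0.57.

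**Step 2: compare the hazard ratio with the medians.** 4.0/6.8 = 0.588. In the other direction, 4.0/0.57 = 7.02 months.

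**Step 3: test whether rounding explains it.** The smallest hazard ratio from medians that round to 4.0 and 6.8 is 3.95/6.85 = 0.577. A value that rounds to 0.57 must be below 0.575. The ranges do not meet.

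**Step 4: what 71 events deliver at the stated medians.** ln 0.588 = −0.5306, using the unrounded ratio.

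| | HR 0.57 | HR 0.588 |
|---|---|---|
| Events for 85% power, Schoenfeld | 68.0 (69) | 76.3 (77) |
| Events for 85% power, Freedman | 71.6 (72) | 79.9 (80) |
| Power with 71 events, Schoenfeld | 86.1% | 83.0% |
| Power with 71 events, Freedman | 84.8% | 81.7% |
| Power with 71 events, simulation | 85.6% | 82.4% |

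Whole events are in brackets. Against the planned 71, 85% power at the stated medians needs 6 to 9 more events (77 − 71 and 80 − 71).

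**Step 5: sensitivity to allocation.** With 2:1 allocation, Schoenfeld power with 71 events is 82.9% at HR 0.57 and 79.6% at HR 0.588, and 77 events would be needed at HR 0.57. The plan's figures fit 1:1 better. The mismatch between the hazard ratio and the medians in Step 2 does not depend on allocation.

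**Step 6: the parallel OS statement.** SAP Section 5.3 makes the same kind of translation. There 12.7/19.8 = 0.641, against a stated 0.64, and Schoenfeld power with 78 deaths at HR 0.64 is 75.5%, against a stated 75%. The OS figures reconcile; the PFS figures do not.

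**The case against.** The strongest reply is that the SAP ties its power to the hazard ratio, and that claim is right. The error lies in the explanatory translation into medians; the alpha level, the test, the 71-event trigger and the analysis do not use it. This stands, and it is why the point is one of reporting and not of a faulty design.

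The effect is also small. The loss against 85% is 2.0 to 3.3 points, while the choice between Schoenfeld and Freedman alone moves power by about 1.3 points. In a randomized phase 2 trial tested at two-sided 0.2, no decision is likely to turn on it. This also stands.

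Further, 71 is a minimum. On the SAP's own timeline (9 months of accrual plus 6 more), with the stated medians and 1:1 allocation, about 77 events would be expected from 105 subjects by month 15. With 77 events at HR 0.588, power is 85.2% (Schoenfeld) or 84.0% (Freedman). That is a real mitigation if the cut-off is set by the calendar, but the stated trigger permits analysis at exactly 71.

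Finally, the most favourable unrounded medians give HR 0.577, for which Schoenfeld requires 71 events and gives 85.0% power. Loose reporting of one figure is thus a plausible origin. It would still leave 0.57 misstated, since 0.577 rounds to 0.58.

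**Conclusion.** The concern holds. Under the SAP's exponential assumption, HR 0.57 and medians of 4.0 and 6.8 months cannot both be the design target. The 71 events and 85% power belong to HR 0.57, which means 4.0 versus 7.0 months. For 4.0 versus 6.8 months, 71 events give 81.7% to 83.0% power, and 85% would take 77 to 80 events. The power and event figures rest on 1:1 allocation, proportional hazards and the absence of a stated sample size formula, hence the ranges; the inconsistency itself rests only on the exponential assumption. It does not threaten the validity of the trial, but it should be corrected because it misstates the target effect of the primary endpoint.

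**What to change.** Reword the sentence in SAP Section 5.1 so that the three figures agree, leaving the event target at 71. There are two consistent versions, and the sponsor should choose the one that reflects its intended target:

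- HR 0.57, corresponding to median PFS of 4.0 versus 7.0 months, with about 85% power from 71 events; or
- HR 0.588, corresponding to median PFS of 4.0 versus 6.8 months, with about 82–83% power from 71 events.

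It would help to name the sample size method and the allocation ratio in the same paragraph if they are not given elsewhere. The protocol's sample size text is redacted and could not be compared; if it carries the same figures, it should be brought into line. The cost is one sentence and a slightly less favourable target or power. No extra patients, events or follow-up are needed.
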